- 3. Arrhythmic myocarditis is largely underdiagnosed and uninvestigated. Importantly, myocarditis presenting with arrhythmias requires specific diagnostic, prognostic and therapeutic considerations [2]. At our hospital, which is an international referral center for ventricular arrhythmias management and ablation, a relevant number of patients with unexplained arrhythmias had myocarditis as underlying aetiology. Our experience may considerably improve knowledge and management of arrhythmic myocarditis.
- 4. The role of CMR, as well as alternative nonivasive imaging techniques, in defining myocarditis healing is a relevant issue. In particular, optimal timing for follow-up diagnostic reassessment is still to be defined, in patients with myocarditis at different inflammatory stages, either with or without aetiology-dependent treatment [4,7].
- 5. Uniformly-designed studies are lacking, to compare myocarditis among different patient subgroups, differing by variables like: clinical presentations, myocarditis stage, associated cardiac or extra-cardiac diseases, aetiology-based treatment, associated arrhythmic manifestations, diagnostic workup, and devices or ablation treatment [8,9,10].

AIMS

Our study has multiple aims (full detail in Table 1).

- 1. To compare EMB with nonivasive diagnostic techniques (CMR, DECT, PET scan, either alone or in association).
- 2. To assess the role of blood biomarkers for identification of aetiology, predisposition, prognosis, response to treatment, inflammatory activity, clinical presentation.
- 3. To describe myocarditis presenting with arrhythmias, with special focus on ventricular arrhythmias at different myocarditis stages and in different clinical contexts. To validate and generalize our model for optimal diagnostic and therapeutical management of arrhythmias in myocarditis patients (given the role of our hospital as an international referral center for arrhythmias ablation and management).

- 4. To evaluate the timing needed for myocarditis healing in different patients subgroups, as assessed by nonivasive imaging techniques (CMR, DECT, PET scan), either alone or in association.
- 5. To compare patients subgroups of myocarditis, in terms of epidemiology, aetiology, prognosis, and diagnostic-therapeutical strategies. Among the others, the main study subgroups will be:
 - A. Arrhythmic vs. non-arrhythmic myocarditis.
 - B. Arrhythmic myocarditis subgroups.

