All patients with myocarditis (or any alternative final diagnosis), will undergo standard cardiological optimal medical treatment (COMT), as indicated. By converse, aetiology-dependent treatment will be performed only in patients with a final diagnosis of any *active* (acute, fulminant, chronic active) myocarditis of defined aetiology (EMB-proved). Multidisciplinary assessment, including infective disease specialists (in viral/infective myocarditis), immunologists (in non-infective/autoimmune myocarditis) or any other specialist as needed, will be used to identify indications to treatment, drug choice (either approved or with a justified off-lable indication), treatment duration and safety profile, aiming at the best patients' interest. Toxic myocarditis will be treated accordingly, by evaluating the opportunity of withdrawing pathogenic noxa.

This protocol will not interfere with local best clinical practice.

Patients with *non-active* myocarditis (previous or healed) or with non-myocarditis, will undergo "standard FU" (see below). Patients with *active* myocarditis will undergo "intensive FU" (see below).

Independently of FU modalities, diagnostic reassessment will be considered in the presence of at least one of the following *instability* criteria: a) new unexplained cardiac symptoms (dypnoea, chest pain, syncope, palpitation); b) new unexplained increase in troponin or natriuretic peptides; c) new imaging abnormal signs; d) new unexplained clinically relevant arrhythmias. Diagnostic reassessment will include second-level imaging and/or EMB, as shown above. Subsequent therapeutical workup will be in line with the above explanations. In stable patients or undergone myocarditis healing, exercise stress test will be obtained, whenever possible.

Panel B - Diagnostic and therapeutical workup of patients with arrhythmias

In parallel with (and independently of) Panel A content, patients with arrhythmias (group A) will undergo specific diagnostic and therapeutical management for arrhythmias, as a result of the integration between international guidelines recommendations and the experience of a third-level center international referral center (San Raffaele Hospital, Milan) for arrhythmia management and ablation.

To oversimplify, 4 groups of patients will be considered.

1. Group 1: major ventricular arrhythmias (haemodynamically unstable VT, hu-VT; ventricular fibrillation, VF).

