	arrhythmias during FU)				• • •	Identification of optimal timing for any electrophysiological/arrhythmologic procedure Role of pharmacological antiarrhythmic treatment Role of aetiology-specific treatment on arrhythmic outcomes Identification of criteria for device implants (PM, ICD, S-ICD, CRT-D) in myocarditis patients Validation of therapeutic strategies and their optimal timing in patients with supraventricular arrhythmias, bradyarrhythmias, or ventricular arrhythmias Correlation between arrhytmia type/features with any other diagnostic exam performed at baseline or during FU (mainly EMB, CMR/DECT/PET, echocardiogram, stress tests,
					•	blood exams, genetic/blood/tissue/cell biomarkers) Indications and timing for device (ICD, CRT-D) implant in primary prevention, based on multiparametric risk assessment, and in relation to different general and aetiology- dependent treatments Other analyses
4	Evaluation of healing timing in myocarditis	500	•	Any degree of recovery by 3, 6, 9, 12 and > 12 months	• • • • •	Comparison of healing times in treated vs. untreated patients Correlations between healing times and clinical presentation types Correlations between healing times and any biomarker Correlations between healing times and any outcomes Validation of exercise stress test role after myocarditis healing Evaluation of PET scan or other diagnostic techniques as alternatives to CMR in special populations Other analyses
5	 Subrgoup analyses A. A vs. NA groups B. A myocarditis subgroups C. NA myocarditis subgroups (including fulminant) D. Infective vs. autoimmune vs. toxic forms E. Tretaed by aetiology- driven therapy vs. standard cardiological treatment 	500 (hugely variable in each subanalys is)	•	Differences in major outcomes	• • • • • •	Differences in minor outcomes Differences in any biomarker Differences in any diagnostic exam Differences in aetiology Differences in predisposition Differences in predisposition Differences in inflammatory activity Differences in pericardial involvement Differences in systemic involvement Differences in systemic involvement Differences in arrhythmias types and features Differences in clinical presentation Differences in treatment response, including novel treatments Validation of local aetiology/pathophysiology- dependent treatments (group E)

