 F. Different myocarditis stages and differential diagnoses G. Isolated vs. in the context o a systemic disease or genetic disease H. Myocarditis vs. perimyocardis/ myopericarditis 	 Validation of biomarkers and imaging techniques in monitoring response to treatment (group E) Identification of optimal follow-up timeline Other analyses
-------------------------------------------------------------------------------------------------------------------------------------------------------------------------------------------------------------------------------------------------------	-------------------------------------------------------------------------------------------------------------------------------------------------------------------------------------------------

FOLLOW-UP VARIABLES

Any quantitative and qualitative parameters detectable by medical history, objetcive examination, biomarkers, 12-leads ECG, signal averaged ECG, continuous telemonitoring (during nwe hospitalization or in device carriers), Holter ECG (at least 24-hours, possibly 12-leads), color Doppler transthoracic echocardiogram, coronary angiography or CT scan, stress tests, CMR, DECT, PET scan (alone or in association/fusion), genetic tests, tilting test, electrophysiological study (either invasive or nonivasive), electroanatomical map, any other imaging or laboratory exam identified as clinically-relevant.

FOLLOW-UP TIMELINE

A clinical time zero (t0) will be considered as the start point for FU. t0 indicates the timing of myocarditis diagnosis, as assessed by EMB (first choice) or by imaging techniques (secondo choice).

FU calendar will be variable based on clinical indications. As a general line, intensive FU will be planned for the first two years (month 3, month 6, month 9, month 12, month 18, month 24). For patients needing a strict control for relevant clinical issues, minimal FU reassessment is set at 2 weeks timespan. In the absence of clinical issues, from month 24 FU will be performed every 6-12 months up to the end of the study.

FOLLOW-UP EXAMS

- Standard FU: cardiological (or multidiciplinary) assessment 1-2/y with blood exams (at least troponin, natriuretic peptides, and inflammatory indexes), 12-leads ECG, Holter ECG monitoring, device interrogation (in device carriers), and color Doppler transthoracic echocardiogram. Second-level imaging techniques (CMR, DECT, PET scan) or other exams will be performed based on clinical indications.

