- Intensive FU: cardiological (or multidiciplinary) assessment 1-2/y with blood exams (at least troponin, natriuretic peptides, and inflammatory indexes), 12-leads ECG, Holter

ECG monitoring, device interrogation (in device carriers), and color Doppler transthoracic echocardiogram. Minimal reassessment timespan is 2 weeks. At least one second-level imaging techniques (CMR, DECT, PET scan) will be performed by 12 months (approximately at 3, 6, 9, or 12 months based on clinical indications). Exercise stress test will be performed whenever clinically indicated, usually not before proved myocarditis healing. Other exams will be performed based on clinical indications.

STUDY DURATION

Estimated study duration is 23 years (from Jaunary 2013 to December 2035). In detail:

- Retrospective enrollment: from January 2013 to local institute review board approval.
- Prospective enrollment: from local institute review board approval to Dicember 2025 (estimated enrollment end).
- FU duration per patient: 10 years.
- Estimated last FU for last enrolled patient: December 2035.

CONFOUNDING FACTORS

Not applicable.

EPIDEMIOLOGIC DATA

Because of multiple clinical presentations and heterogeneous diagnostic techniques, myocarditis incidence is widely variable [1].

At our institution, the mean rate of clinically suspected myocarditis is not inferior to 4 new cases/month. Epidemiology may be different at other centers.

Target numbers reported in Table 1 are reasonable.

DATA COLLECTION AND STATISTICAL ANALYSIS

Two enrollment modalities are accepted for this study: 1) prospective enrollment: at myocarditis diagnosis (following local institute review board approval); 2) retrospective enrollment: during FU of myocarditis patients (diagnosed before local institute review board approval).

Considering incidence rate, local and general epidemiology, enrollment of 1000 myocarditis cases by December 20205 is expected, including retrospective and prospective enrollment. For aim 1, 95% confidence intervals of 81-89% and of 75-85% are estimated for EMB and CMR, with 85% and 80% sensitivity, respectively. These data are consistent with updated knowledge. EMB will be considered as the diagnostic gold standard, as indicated [1].

Both baseline and FU data will be collected for each enrolled patient. CRF form reports the main study variables, in the form of an Excel document.

Statistical analyses will be performed by certified programs (i.e. SPSS).

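### Aim 4's recovery classes, above all the > 12 months class, are not supported by the imaging schedule: late recovery is ascertained selectively, with a bias of unknown size and sign

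*Protocol*

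**What the plan says.** Under AIMS, item 4, healing time is to be assessed by non-invasive imaging (CMR, DECT, PET). Table 1 lists aim 4 as "Evaluation of healing timing in myocarditis", with a target of 500 patients and the primary variable "Any degree of recovery by 3, 6, 9, 12 and > 12 months".

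FOLLOW-UP EXAMS sets what is actually scanned:

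- **Intensive follow-up** (active myocarditis): "At least one second-level imaging techniques (CMR, DECT, PET scan) will be performed by 12 months", timed "approximately at 3, 6, 9, or 12 months based on clinical indications". Beyond that, "Other exams will be performed based on clinical indications".
- **Standard follow-up** (non-active myocarditis or another diagnosis): "Second-level imaging techniques (CMR, DECT, PET scan) or other exams will be performed based on clinical indications".

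FOLLOW-UP TIMELINE adds visits at months 18 and 24 and then every 6 to 12 months. STUDY DURATION gives 10 years of follow-up per patient. The tests listed for these visits include echocardiography but no required CMR, DECT or PET.

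The one itemised trigger for further imaging is in STUDY DESIGN, Panel A: "diagnostic reassessment will be considered in the presence of at least one of the following" instability criteria, namely new symptoms, a biomarker rise, new imaging abnormalities or new arrhythmias. The reassessment may be imaging, biopsy or both.

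**The concern.** The last class of a primary variable has no planned assessment behind it. A patient still unhealed at the last scan up to month 12 who then recovers quietly need never be scanned again, so that recovery may never be recorded. The itemised triggers are all signs of worsening, and one of them is itself an imaging finding, so scanning can depend on the outcome being measured.

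The weakness does not begin at month 12. One scan at a clinically chosen time satisfies the rule for the whole first year, so the 3, 6, 9 and 12 month classes are thinly supported as well.

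At stake are the recovery curve itself and the analyses built on it. Table 1 uses healing time to compare treated with untreated patients and to correlate with presentation, biomarkers and outcomes.

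**Working it through.** The protocol gives no healing rate, scan rate or sample-size derivation for aim 4, so there is no figure of its own to reproduce. The check has two parts.

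**1. What one required scan can classify.** Suppose a patient has only the required scan, and suppose recovery, once present, lasts.

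| Scan at | Result | What is known |
|---|---|---|
| Month 3 | Recovered | Recovered by 3, hence by 6, 9 and 12 |
| Month 3 | Not recovered | Not by 3; later classes unknown |
| Month 6 or 9 | Recovered | Recovered by that month; earlier classes unknown |
| Month 6 or 9 | Not recovered | Not by that month; later classes unknown |
| Month 12 | Recovered | Recovered by 12; 3, 6 and 9 unknown |
| Month 12 | Not recovered | Not by 12; > 12 unknown |

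Only the first and last rows fill all four classes up to month 12. No patient who is unhealed at the required scan has a > 12 months result.

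**2. How selective late scanning distorts the > 12 months figure.** All rates here are assumptions. Take patients unhealed at month 12.

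- w = 0.20 later worsen.
- Late recovery is 0.50 in stable and 0.10 in worsened patients.
- Worsened patients are scanned with probability 0.9, stable patients with probability s.

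True late recovery = 0.8 × 0.50 + 0.2 × 0.10 = 0.42.

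Recovery among scanned = (0.2 × 0.9 × 0.10 + 0.8 × s × 0.50) / (0.2 × 0.9 + 0.8 × s) = (0.018 + 0.40s) / (0.18 + 0.80s).

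Recorded recovery among all = 0.018 + 0.40s.

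Worsened share of those scanned = 0.18 / (0.18 + 0.80s).

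| s | Among scanned | Recorded among all | Worsened share of scanned |
|---|---|---|---|
| 0 | 10% | 1.8% | 100% |
| 0.1 | 0.058/0.26 = 22% | 5.8% | 69% |
| 0.3 | 0.138/0.42 = 33% | 13.8% | 43% |
| 0.6 | 0.258/0.66 = 39% | 25.8% | 27% |
| 0.9 | 0.378/0.90 = 42% | 37.8% | 20% |

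Varying w at s = 0.1: with w = 0.10 the true value is 46% and 30% is seen among scanned; with w = 0.30 the true value is 38% and 18% is seen.

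**Reversed sign.** Keep w = 0.20, but let stable patients be scanned mainly to confirm healing: 0.6 if healed, 0.2 if not.

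- Recorded recoveries: 0.018 + 0.8 × 0.5 × 0.6 = 0.258.
- Scanned: 0.18 + 0.8 × (0.5 × 0.6 + 0.5 × 0.2) = 0.50.
- Among scanned: 0.258/0.50 = 52%, against a true 42%.
- Among all: 25.8%, still below 42%.

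**Bounds for the unscanned.** At s = 0.1, 26% are scanned and 74% are not. The bounds run from 5.8% (no unscanned patient recovered) to 5.8% + 74% = 79.8% (all recovered). In the reversed-sign case they run from 25.8% to 75.8%. Both contain 42%, and their width shows how little the late scans alone can say.

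**The case against.** A reader might infer that the reason for scanning switches at month 12 from routine to deterioration, so that the > 12 months class is read mainly in patients who got worse and late healing is understated. The protocol does not support this, for three reasons.

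- Panel A applies the instability criteria whatever the follow-up mode, so they operate before and after month 12 alike. The scan within the first year is also clinically timed.
- Clinical indication is left open and can cover patients who are doing well. Exercise testing usually waits for proven healing, and Panel B reconsiders rhythm control once myocarditis has healed. Instability only means that reassessment is considered, and that may be a biopsy rather than a scan.
- In the illustration at 20% worsening, worsened patients are a majority of those scanned at s = 0.1 but not at s = 0.3, and confirmatory scanning reverses the sign among scanned patients.

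It is also fair to say that clinically driven imaging is the declared observational design, that censoring rules may sit in an SAP not available here, and that the CRF is a separate file which may already hold a reason for each scan.

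What stands is narrower but sufficient. The protocol itself sets a primary variable with classes that its own imaging schedule does not require anyone to assess. An SAP cannot recover a reason for scanning that was never collected.

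**Conclusion.** The point holds as a mismatch between aim 4's primary variable and the imaging schedule. Recovery > 12 months is ascertained selectively, and the 3 to 12 month classes rest on as little as one clinically timed scan.

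The direction is conditional. Late recovery is understated among scanned patients if instability drives the late scans. It is understated among all patients if unscanned patients count as not recovered and some of them have healed. It can be overstated among scanned patients if late scans mainly confirm healing. Under the stated assumptions a true 42% reads as 10% to 52% among those scanned, and as 1.8% to 37.8% among all. These figures show what could happen; they do not estimate what will, and the protocol fixes neither size nor sign. The change is worth making because it is cheap and limits the claim to what the schedule can support.

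**What to change.** Reconcile Table 1, aim 4, with FOLLOW-UP EXAMS, without adding scans:

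1. Record the reason for every follow-up second-level scan, before and after month 12: planned reassessment, confirmation of healing, or instability criterion.
2. Limit the primary healing-time series to the window up to month 12. Treat healing as interval-censored between scans and censor unhealed patients at their last scan. State that scan timing is clinically chosen, so the censoring may be informative.
3. Report > 12 months recovery descriptively only, from all late scans split by reason. Give the number scanned out of all patients unhealed at their last scan, with lower and upper bounds for the unscanned.
4. Do not restrict the late figure to scans not triggered by instability. That selects in the opposite direction: in the illustration, stable patients scanned regardless of healing give 50% against a true 42%. Do not present the late figure as a continuation of the 3 to 12 month series.

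Cost: the > 12 months class loses its primary status, and one CRF field is added if it is not already there. Patient care does not change.

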 - C. Non-arrhythmic myocarditis subrgoups (i.e.: fulminant, acute coronary syndrome-like, pericarditis-like, heart failure, nonischaemic dilated /hypokynetic cardiomyopathies of unknown aetiology...).
 - D. Infectious vs. aoutoimmune vs. toxic myocarditis.
 - E. Myocarditis treated by aetiology-based treatment vs. isolated cardiac medical treatment.
 - F. Myocarditis at different disease stages: acute, hyperacute, fulminant, chronic active, post-inflammatory, or active vs. previous vs. non-myocarditis.
 - G. Myocarditis presenting as organ-specific diseases vs. in the context of a genetic disorder or systemic disease.
 - H. Myocardits vs. peri-myocarditis/myo-pericarditis.
 - I. Other analyses.

STUDY DESIGN

Our study, previously designed as a single-center experience, is multicenter, observational and both retrospective and prospective.

Retrospective phase includes all clinical data occurring before the index event (hospitalization or clinically suspected myocarditis) and myocarditis diagnosis. Prospective phase includes all data following index event and myocarditis diagnosis.

Any adult patient with clinically suspected myocarditis, of any clinical presentation and any degree of severity, will be considered as suitable for study enrollment.

Patients will undergo diagnostic and therapeutical strategies considered as clinically indicated in a patient-tailored manner, as suggested by international guidelines recommendations and best local clinical practice. Patients will be free of either accepting or refusing any diagnostic or therapeutical proposal. Whenever accepted, data will be simply collected and analyzed.

Based on clinical presentation, patients will be divided into two groups, arrhthmic (group A) and non-arrhythmic (group NA, including any other clinical presentation).

Independently of A/NA groups, all patients will undergo optimal diagnostic and therapeutic strategies, as summarized in panel A. In parallel, special diagnostic and therapeutical strategies will be performed in patients with arrhythmic presentation or evidence of arrhythmias, as shown in panel B. Proposed flowcharts (panels A and B) represent only an approximate algorithm. Exceptions can be made in single cases, based on clinical indications.

Panel A – Diagnostic and therapeutical workup in all patients.

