Data will be presented as mean/median and standard deviation/interquartile range, or as contingency tables, depending on variables type and distribution. Parametric and non-parametric tests will be used accordingly. Confidence intervals will be set at 95%. Statistical significance threshold will be set at p < 0.05. Regression models will be used for univariable and multivariable risk stratification and survival analyses.

Either in all patients or in subgroups, appropriate statistical tests will be used for general and specific analyses, as needed to address each study aim (Table 1).

ETHICAL ISSUES

Our study will be performed in accordance with Helsinki Declaration and current laws regarding observational prospective and retrospective studies.

Diagnostic and therapeutical workup will not differ from daily clinical practice a tour hospital, as the result of updated international scientific evidence, integrated by the experience of a referral center for myocarditis and arrhythmias management, aiming at the best patients' interest. Follow-up timeline and diagnostic exams will be required as clinically needed. No randomization procedures will be performed. Patient grouping will be "spontaneous", based on clinical features and personalized overall workup. This study will respect the autonomy principle for any patient. At any time, patients will be free to accept or refuse any diagnostic or therapeutical proposal. As in daily clinical practice, critical or exceptional diagnostic and therapeutical options will be discussed in a multisiciplinary team and shared with patients, as needed. Per protocol, data will be simply collected and analyzed, without interfering with the best clinical practice. Thus, for any diagnostic exam or treatment, no special adverse reactions are expected, as compared to what observed in daily clinical practice.

Written informed consent will be obtained for any enrolled patient. No physical or psychosocial risks are expected regarding study procedures, informed consent, or authorization to use personal data.

Institutional review board evaluation is necessary to approve the present study protocol.

All data will be made anonymous. Analyses results will be published in international medical journals with impact factors.

REFERENCES

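### The protocol declares confounding not applicable, but its treatment comparisons (Aim 5E and secondary items in Aims 3 and 4) are open to confounding by indication

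*Protocol*

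**What the plan says.** The Confounding Factors section of the protocol reads, in full, "Not applicable".

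Other sections describe how the treatment groups arise:

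- Study Design calls the study multicentre and observational. It lets patients decline any proposed test or treatment, and says that the flowcharts "represent only an approximate algorithm".
- Study Design, Panel A, states that "aetiology-dependent treatment will be performed only in patients with a final diagnosis of any" active myocarditis whose aetiology is defined and biopsy-proved. A multidisciplinary team identifies the indication, the drug and the duration.
- Ethical Issues rules out randomisation and says that groups form by themselves from clinical features and individual workup.

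The treatment comparisons are these:

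- Aims, item 5E: "Myocarditis treated by aetiology-based treatment vs. isolated cardiac medical treatment". The primary variable of Aim 5 in Table 1 is "Differences in major outcomes". A secondary variable is the validation of local aetiology-dependent treatments.
- Table 1, Aim 3, secondary: "Role of aetiology-specific treatment on arrhythmic outcomes".
- Table 1, Aim 4, secondary: "Comparison of healing times in treated vs. untreated patients".

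On method, Data Collection and Statistical Analysis says "Regression models will be used for univariable and multivariable risk stratification and survival analyses" and promises suitable tests for each aim in Table 1. Variables and Endpoints adds multiparametric modelling of prognosis and treatment response. None of these sentences names confounding or a treatment contrast.

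**The concern.** The factors that decide who receives aetiology-based treatment are likely to bear on death, transplantation, malignant arrhythmia and end-stage heart failure in their own right. A crude comparison of treated and untreated patients would then mix the effect of the treatment with the characteristics of those selected for it. An analyst who takes the entry at its word has no reason to adjust. A difference in major outcomes could then be reported as validating a treatment when it reflects who was treated. The same risk attaches to the secondary treatment items in Aims 3 and 4. Patient care is not affected.

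**Working it through.** The protocol gives no effect size, event rate or group size for 5E, only 500 patients for the whole of Aim 5, so there is no planned figure to reproduce. The finding rests on setting the sections side by side.

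**Step 1: does the entry fit the design?** Confounding by indication needs two things: treatment given according to patient characteristics, and outcomes compared by treatment. Panel A and Ethical Issues supply the first. Item 5E with the Aim 5 primary variable supplies the second. The entry therefore contradicts the rest of the protocol.

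**Step 2: how large could the bias be?** This is an illustration only, and every input is assumed. Let *p* be the share of treated patients with active disease, *f* the share of comparators with active disease, and *H* the hazard ratio for active disease. With no treatment effect,

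crude HR = (pH + 1 − p) / (fH + 1 − f).

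For example, with p = 1, H = 2, f = 0.30: 2 / (0.60 + 0.70) = 2 / 1.30 = 1.54.

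| p | H | f = 0.10 | 0.30 | 0.50 | 0.75 |
|---|---|---|---|---|---|
| 1.0 | 1.5 | 1.43 | 1.30 | 1.20 | 1.09 |
| 1.0 | 2 | 1.82 | 1.54 | 1.33 | 1.14 |
| 1.0 | 3 | 2.50 | 1.88 | 1.50 | 1.20 |
| 1.0 | 0.5 | 0.53 | 0.59 | 0.67 | 0.80 |
| 0.9 | 2 | 1.73 | 1.46 | 1.27 | 1.09 |
| 0.9 | 0.5 | 0.58 | 0.65 | 0.73 | 0.88 |

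The case f = p = 1 also belongs in the range. The ratio is then H/H = 1.00 for every H, so disease activity causes no bias if every comparator has active disease.

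**Step 3: could it produce a false positive?** Assume a 10% risk in non-active disease, a doubled risk in active disease, 250 patients per group, all treated patients active and no treatment effect. If half the comparators are active, the risks are 20% and 15%, and p < 0.05 occurs about 31% of the time. If 30% are active, the risks are 20% and 13%, and it occurs about 56% of the time.

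**Step 4: does adjustment help?** A simulation used 400,000 patients, 40% treated, no treatment effect, a 15% ten-year base risk, H = 2, p = 0.9, and activity as the only confounder. The crude ratio was 1.47 at f = 0.30 and 1.09 at f = 0.75. Adjusting for activity gave 1.00 and 0.99. This is a best case, because real adjustment leaves residual confounding.

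**Step 5: which patients carry the information?** Assume 500 patients, 40% treated, all treated active, f = 0.30, base risk 15%, H = 2.

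- Risk in active disease: 1 − 0.85² = 0.2775.
- Events, treated: 200 × 0.2775 = 55.5.
- Events, active comparators: 90 × 0.2775 = 25.0.
- Events, non-active comparators: 210 × 0.15 = 31.5.

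The non-active stratum contains no treated patients, so a model adjusted for activity learns the treatment effect from the active stratum alone. SE(log HR) ≈ √(1/55.5 + 1/25.0) = 0.241, and the 95% interval is the estimate times or divided by exp(1.96 × 0.241) = 1.60. That holds both for the adjusted model in all patients and for the analysis restricted to active patients. The crude contrast gives √(1/55.5 + 1/56.5) = 0.189, a factor of 1.45, but it is the biased one.

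**The case against.** The best defence is that adjustment is already available. The statistics section plans multivariable survival regression and tests suited to each aim, and the endpoint section plans prognostic modelling. Covariates and model form commonly belong in a statistical analysis plan, which is not shown. Aim 5 is framed mainly as a comparison of subgroups; 5E is one of eight contrasts, and the other seven do not compare treatments. Most of this stands. It limits the weight of the point and leaves model detail to the analysis plan. It does not make the entry correct, because no sentence links the regression to a treatment contrast or qualifies the declaration.

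Three stronger readings are tempting, and the protocol supports none of them.

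- *That 5E will be analysed crude.* Nothing says so.
- *That the result will be biased by a known amount or in a known direction.* The composition of the 5E comparators is not stated. The activity bias is nil if they are all active, and it reverses if active disease carries the better prognosis.
- *That the groups cannot overlap because treatment follows a strict rule.* The flowcharts are approximate and patients may refuse, so eligible untreated patients can exist; how many is unknown.

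For Aim 4 the activity mechanism is probably weak. Healing presupposes active disease, and the imaging due by 12 months belongs to intensive follow-up, which Panel A assigns to active myocarditis. Aetiology and severity remain possible confounders there.

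**Conclusion.** The entry is wrong for the treatment contrasts and should be corrected. That conclusion needs only the protocol's text and no assumed figure. The bias itself cannot be sized. In the Step 2 table it runs from 0.53 to 2.50 under assumed inputs, with 1.00 when all comparators are active, and it concerns disease activity alone. Aetiology, severity, biopsy status and centre could confound even where activity does not. The point is worth fixing before analysis because the remedy is cheap and the contrasts are meant to inform treatment. It is not evidence that any result is or will be invalid.

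**What to change.** Replace "Not applicable" with a statement that 5E, the role of aetiology-specific treatment in Aim 3 and the treated-versus-untreated healing times in Aim 4 are subject to confounding by indication, in Aim 4 mainly through aetiology and severity. Add that:

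- these contrasts will be estimated with the multivariable regression already planned, adjusted for recorded baseline disease stage or activity, presentation, aetiology and ventricular function;
- unadjusted contrasts are descriptive only;
- residual confounding is acknowledged;
- 5E will also be reported among patients who meet Panel A's own treatment criteria. This should not rank below the all-patient model, because non-eligible patients add little or nothing on the treatment effect once activity and aetiology are adjusted for (Step 5).

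Model details can stay with the statistical analysis plan.

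The cost is a few sentences, a little more analysis work, and wider intervals than the crude contrast (a factor of 1.60 against 1.45 in the illustration). The case report form is not shown, so covariate availability needs checking. Aetiology may be unknown in patients without a biopsy, and their handling should be stated. Care does not change.
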